4.1.2. Exclusion criteria

Patients meeting any of the following criteria will not be included in the study:

- 1. Having a diagnosis of valvular atrial fibrillation, post-operative atrial fibrillation, rheumatic atrial fibrillation or mechanical-valvular atrial fibrillation during the baseline and post-index period
- 2. Having a procedure of prosthetic heart valve during the baseline period
- 3. Having a cardiac surgery procedure record during the baseline period
- 4. Having a diagnosis of venous thromboembolism during the baseline period
- 5. Having a hemodialysis during the baseline period
- 6. *Female patients with pregnancy during the baseline and follow-up period*
- 7. Patients prescribed apixaban other than approved daily dose (<5 mg or >10 mg)
- 8. Patients prescribed OACs during baseline period

4.1.3. Definitions

4.1.3.1. Follow-up period

Follow-up time period starts from the next day of the index date, and ends depending on following outcomes which observed first.

- 1. Major bleeding when the target outcome for the analysis is major bleeding.
- 2. Composite of (ischemic or hemorrhagic) stroke and SE when the target outcome for the analysis is the composite endpoint.
- 3. Discontinuation of apixaban or warfarin: The index treatment will be considered to be "discontinued" if apixaban or warfarin is not prescribed within 45 days after prescription refill date (calculated from the last refill date plus days of supply) of apixaban or warfarin, even though the patient has >1 medical encounter records after more than 45 days following the prescription refill date. The supposed prescription refill date is regarded as the last day of the follow-up for discontinued patients.
- 4. Switching from apixaban or warfarin: The index treatment is regarded as "switched" if the OAC is prescribed within 45 days after prescription refill date of apixaban or warfarin when the patient has 1> medical encounter records after more than 45 days following the prescription refill date. The switched day is regarded as the last day of the follow-up for the switched patients.
- 5. Withdrawal from the database: The patients are regarded as "withdrawal" from the database if apixaban or warfarin is not prescribed within 45 days after prescription refill date of the apixaban or warfarin and there is no data of the patient on the database after prescription refill date. The last medical encounter is regard as the last day of the follow-up for patients withdrawn from the database.
- 6. An elapse of 2 years from the index date without any of the event above.

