7.1.8. Sensitivity analysis

For the primary effectiveness and safety analysis, E-values¹⁰ (evidence for causality) will be calculated based on calculated hazard ratios and 95% confident intervals to assess the extent of unmeasured confounding. The E-value is defined as the minimum strength of association for an unmeasured confounder with both the treatment and the outcome to explain away the observed significant (if any) treatment-outcome association.

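### In the 45-day refill gap, whether a major bleed or stroke/SE counts depends on what happens to the patient afterwards

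*SAP*

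**What the plan says.** SAP 4.1.3.1 lists six ways in which follow-up can end. Protocol 9.2 has the same list. Follow-up "ends depending on following outcomes which observed first".

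- **Items 1 and 2** end follow-up at the target outcome.
- **Item 3, discontinuation**, applies "if apixaban or warfarin is not prescribed within 45 days after prescription refill date (calculated from the last refill date plus days of supply". It carries a further condition, "even though the patient has >1 medical encounter records after more than 45 days following the prescription refill date". The end date is then set: "The supposed prescription refill date is regarded as the last day of the follow-up for discontinued patients".
- **Item 4, switching:** "The switched day is regarded as the last day of the follow-up for the switched patients". I read the drug prescribed in this item as an oral anticoagulant other than the index drug.
- **Item 5, withdrawal**, requires that "there is no data of the patient on the database after prescription refill date".
- **Item 6** caps follow-up at 2 years.

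A patient who refills within the 45 days meets none of items 3 to 5 at that point and stays at risk through the gap. SAP 7.1.8 is the whole sensitivity plan: "E-values¹⁰ (evidence for causality) will be calculated based on calculated hazard ratios". No section varies the 45 days or the censoring date, and the limitations in protocol 9.9 do not mention either.

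**The concern.** Ending follow-up for everyone at the end of supply would be a choice of exposure window. So would ending it for everyone 45 days later. Item 3 does neither. Gap time counts for patients who go on to refill or switch and is removed for those who do not, and this is known only by looking forward from the gap.

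A hospitalised bleed or a stroke can itself be the reason why the drug is not refilled. The gap time that is kept then belongs to patients selected for resuming treatment, while the events that ended treatment in the gap are converted to event-free censoring. This is outcome-dependent censoring. It affects the hazard ratio, the Kaplan-Meier curves and the incidence rates of both primary endpoints.

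**Working it through.** **Date check.** Suppose supply ends on day 30, so the 45-day gap ends on day 75.

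| Case | Item that applies | Result |
|---|---|---|
| Bleed day 50, refill day 60 | not discontinued | counted on day 50 |
| Bleed day 50, switch day 60, later encounters | 4 | counted on day 50 |
| Bleed day 50, no refill, more than one encounter after day 75 | 3 | follow-up ends day 30; bleed dropped |
| Bleed day 50, death day 55 | neither 3 nor 5 | not defined |
| Bleed day 20 (on supply), never refilled | 1 | counted on day 20 |

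The first and third rows are the same event with opposite results. Item 5 deletes no gap event, because it applies only when nothing is recorded after the refill date.

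**Inputs from the plan.** SAP 7.1.9 gives a hazard ratio of 0.7, a warfarin major-bleeding rate of 3.77%/year and 246 events. The event count reproduces: 4 × (1.960 + 0.842)² / (ln 0.7)² = 246.8, truncated in the SAP to 246. The plan gives no figure for the share of events in gaps or for stopping after an event, so everything below that uses them is assumed.

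**When deletion biases and when it does not.** Let p be the share of events and t the share of person-time deleted in an arm. Approximately:

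HR multiplier = [(1 − pA)/(1 − pW)] × [(1 − tW)/(1 − tA)]

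If p = t within each arm, the multiplier is 1 whatever the shares. For example, with apixaban losing 3% and warfarin 15% of both events and time, (0.97/0.85) × (0.85/0.97) = 1. Patients who stop for unrelated reasons behave roughly like this.

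Patients who stop because of the event do not. At 3.77%/year there is one event per 1/0.0377 = 26.5 person-years, but dropping a gap event removes at most 45/365.25 = 0.12 years. Here p far exceeds t, and t can be neglected.

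**Illustration for event-driven stopping.** Let f be the share of events falling in gaps that would otherwise have been refilled, and q the share of those after which the patient does not refill.

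HR multiplier = (1 − f·qA)/(1 − f·qW), applied to 0.70:

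| f | qA = qW | qA 0.7, qW 0.3 | qA 0.3, qW 0.7 |
|---|---|---|---|
| 0.05 | 0.70 | 0.965/0.985 → 0.686 | 0.985/0.965 → 0.715 |
| 0.10 | 0.70 | 0.93/0.97 → 0.671 | 0.97/0.93 → 0.730 |
| 0.20 | 0.70 | 0.86/0.94 → 0.640 | 0.94/0.86 → 0.765 |

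With equal q the hazard ratio stays, but rates fall. At f = 0.10 and q = 0.5, the warfarin rate becomes 3.77 × (1 − 0.05) = 3.58%/year.

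**Simulation of item 3.** Inputs were 3.77%/year, HR 0.7, and the following assumptions: 30- or 60-day supplies, 30–50% late refills averaging 7–12 days, and 4% background stopping per refill.

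- No event-driven stopping: 2.3–5.1% of events were dropped, yet the warfarin rate stayed at 3.77–3.86%/year.
- Stopping probability 0.5–0.8 after a gap event in both arms: about 4–17% of events were dropped and the warfarin rate fell to about 3.3–3.7%/year.
- Counting everyone through refill date plus 45 days: HR 0.68–0.72, which is 0.70 within Monte Carlo noise. The simulation held the hazard constant in the gap, so it says nothing about dilution from off-drug time.

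**The case against.** Censoring at the end of supply is a recognisable on-treatment choice. Adding 45 days assigns some unexposed time and events to the drug. That is true, and it is why the longer window is proposed as a pre-specified sensitivity analysis; making it primary is a trade-off for the sponsor. It does not answer the inconsistency, because refillers and switchers already contribute gap time in the current primary analysis.

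The wording can also be read to keep gap events. Follow-up "ends depending on following outcomes which observed first", and SAP 2.1 and protocol 9.1 likewise stop at the earliest scenario. A bleed on day 50 is seen before discontinuation can be established on day 75. The explicit last-day sentence in item 3 points the other way and is the more natural reading, but the ambiguity is real. Two programmers could obtain different event counts.

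A reader might infer that every event that ends treatment is lost, or that gap events count only after a refill. Neither is so: events during supply end follow-up under items 1 and 2, and gap events before a switch survive under item 4.

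**Conclusion.** The point stands, limited to the gap. Read as written, item 3 makes the counting of a gap event depend on what follows it, on both primary endpoints, and nothing else in the plan corrects this. E-values concern unmeasured confounding, not censoring.

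Rates are understated if events are over-represented in the deleted time. The hazard ratio is biased only if that over-representation differs between drugs. The illustrative range of 0.64 to 0.77 around 0.70 rests on up to 20% of events falling in gaps and on stopping shares of 0.3 against 0.7. None of these comes from the documents.

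A reader might go further and infer that the bias runs toward the null because recorded days of supply are less accurate for warfarin. The documents say nothing about the accuracy of days of supply; protocol 9.9 discusses only INR information and control. A larger share of deleted events on one drug would not be enough in any case, since deleted person-time can offset it.

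Nor does this undermine the sample size. Losing 10% of 246 events leaves 221 and power of about 0.76 at the planned minimum, but SAP 7.1.9 reports more than 10,000 eligible patients on each drug against a larger total requirement of 10,789.

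**What to change.** 1. In SAP 7.1.8, pre-specify for both primary endpoints an analysis in which follow-up for patients without a refill or switch ends at refill date plus 45 days and events up to then count. This is the same window in which refillers are already at risk.
2. In SAP 4.1.3.1, and in the matching text of protocol 9.2, state whether the first-observed rule or the last-day sentence of item 3 governs an event in the gap.
3. Define the end of follow-up for patients with data in the gap who meet neither item 3 nor item 5, such as a death after a gap event, and apply the same 45-day window to them in the added analysis.

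The cost is one extra run per primary endpoint, on data already held, and a few sentences of text. The downside is some off-drug time in the added analysis, which may dilute the hazard ratio. Following everyone to 2 years regardless of stopping or switching would answer a different question and is not needed to settle this point.

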2.1. STUDY DESIGN

This is a retrospective observational study using data from Medical Data Vision Co. Ltd. (MDV Co. Ltd.) database (data set from 1 March, 2011 to 31 Jun, 2021). Among patients registered in the database, patients are selected based on the inclusion and exclusion criteria (see below).

Study measures include: (1) for safety evaluation: major bleeding (primary safety endpoint, defined as any bleeding requiring hospitalization for treatment); (2) for effectiveness evaluation: a composite of ischemic stroke, hemorrhagic stroke or SE (primary effectiveness endpoint).

The primary purpose of this study is to investigate the safety and effectiveness of apixaban compared to warfarin in patients who are prone to bleeding, with at least one known risk factor for bleeding. The analyses will be conducted using the 3-step procedure shown below,

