2.1.2. Data source

The analysis will be based on administrative data from MDV Co. Ltd., a longitudinal database based on health insurance claims and medical records obtained from the hospitals in which the DPC payment system for utilization of both inpatient and outpatient hospital claims (percentage of inpatients is about 20%). The database provides claims data from 449 hospitals (as of Aug 2021) using the DPC system for medical service claims (26% of general hospitals in Japan is under the DPC system) including approximately 36.7 million patient data.

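### Follow-up rule 5 drops event-free supplied days but keeps events in them, and with no data-cut rule it also catches patients still under observation

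*SAP*

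**What the plan says.** SAP 4.1.3.1 lists six ways in which follow-up ends, whichever comes first. Protocol 9.2 carries the same list.

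- Rules 1 and 2 end follow-up at the target outcome, for example "Major bleeding when the target outcome for the analysis is major bleeding".
- Rule 3 (discontinued, with later encounters): "The supposed prescription refill date is regarded as the last day of the follow-up for discontinued patients". That date is "calculated from the last refill date plus days of supply", called supply end below.
- Rule 5 (withdrawn) applies when the index drug is not prescribed within 45 days after supply end and "there is no data of the patient on the database after prescription refill date". Then: "The last medical encounter is regard as the last day of the follow-up for patients withdrawn from the database".
- Rule 6: "An elapse of 2 years from the index date without any of the event above".

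No rule mentions the end of the data, although SAP 2.1 bounds the study by it: "data set from 1 March, 2011 to 31 Jun, 2021". Outcomes come from hospital claims (SAP 5.1 and 5.2), and SAP 2.1.2 describes the source as "a longitudinal database based on health insurance claims and medical records obtained from the hospitals".

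**The concern.** Rule 5 requires that nothing is recorded after supply end, so the last encounter falls on or before supply end. The supplied days after it are removed for event-free patients. An outcome in those same days is a hospital record and ends follow-up under rule 1 or 2, so it counts. Follow-up length therefore depends on the outcome: the numerator keeps events from a period whose event-free time leaves the denominator. Censoring at last contact would be neutral if events after the last preceding visit were also excluded, but no rule excludes them.

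The missing data-cut rule widens the group affected. A patient on drug when the data end, with under two years of follow-up and no record after supply end, meets rule 5 and no other rule.

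At stake are the rates per 1,000 person-years and the Kaplan-Meier curves for both primary endpoints and, if the arms differ in visit or supply pattern, the hazard ratios.

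**Working it through.** **The plan's own figures.** Events for HR 0.7, two-sided 0.05, power 0.80, 1:1: 4 × (1.960 + 0.842)² / (ln 0.7)² = 246.8 (SAP 7.1.9 gives 246). Patients: 246 / ((0.0377 + 0.0250)/2) = 7,847 and 246 / ((0.0277 + 0.0179)/2) = 10,789 (SAP: 7,846 and 10,789). None of these uses the censoring rule, so none changes.

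**The asymmetry in one example.** Two patients have their last visit on day 300 and supply to day 360. One has a recorded bleed on day 320 and contributes 320 days and one event. The other is event-free with no further record and contributes 300 days. At the extreme, a patient with one prescription and no later record has a last encounter on the index date. Follow-up starts the next day, so an event-free patient contributes no time, while a bleed during that first supply counts.

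**Size.** The documents give none of the needed inputs, so all of these are assumptions:

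- Supply equals visit interval, v = 30 or 60 days.
- Yearly hazards of discontinuing/leaving are 0.3/0.3 or 0.4/0.5.
- Entry is uniform over 4 years (recent entry) or 10.3 years (the whole data set).
- Follow-up is capped at two years.

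These give T (mean days to supply end, data cut or event), L (share who left the database) and C (share ending at the cut). A patient who left loses v days. A data-cut patient loses v/2 on average, because the cut falls anywhere within the interval.

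Inflation from data-cut patients = T / (T − C·v/2). Total with every later event captured = T / (T − L·v − C·v/2).

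| v | Entry; hazards | L | C | T | Data-cut part | Total, full capture |
|---|---|---|---|---|---|---|
| 30 | 4 y; 0.3/0.3 | 0.27 | 0.30 | 339 | 339/334.5 = 1.013 | 339/326.4 = 1.039 |
| 30 | 10.3 y; 0.4/0.5 | 0.42 | 0.09 | 319 | 319/317.65 = 1.004 | 319/305.05 = 1.046 |
| 60 | 4 y; 0.3/0.3 | 0.26 | 0.31 | 348 | 348/338.7 = 1.027 | 348/323.1 = 1.077 |
| 60 | 4 y; 0.4/0.5 | 0.36 | 0.25 | 292 | 292/284.5 = 1.026 | 292/262.9 = 1.111 |
| 60 | 10.3 y; 0.3/0.3 | 0.31 | 0.12 | 400 | 400/396.4 = 1.009 | 400/377.8 = 1.059 |
| 60 | 10.3 y; 0.4/0.5 | 0.41 | 0.10 | 330 | 330/327 = 1.009 | 330/302.4 = 1.091 |

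Direct simulation of the six rows gives totals of 1.037, 1.045, 1.075, 1.107, 1.057 and 1.088.

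**If no later event is captured in patients who left.** Their last-encounter censoring is then unbiased and only the data-cut part remains. Supply-end censoring would instead add L·v days in which no event can be seen, a factor of (T − L·v)/T. In the four 60-day rows this is 332.4/348 = 0.955, 270.4/292 = 0.926, 381.4/400 = 0.954 and 305.4/330 = 0.925. A separate simulation at the SAP's bleeding rates, with 52% of patients leaving under rule 5, gives 3.44 against a true 3.77 per 100 person-years (3.44/3.77 = 0.912).

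**Hazard ratio.** The true rate ratio at the SAP's bleeding rates is 2.50/3.77 = 0.663. Simulation with full capture gives:

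- equal 60-day supplies, 52% ending under rule 5: 2.74/4.14 = 0.66, unchanged although both rates are too high;
- warfarin 30 days, apixaban 60 days: 0.675 with 26% ending under rule 5, 0.695 with 52%;
- warfarin 30 days, apixaban 90 days: 0.689 and 0.729.

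**The case against.** The different end dates in rules 3 and 5 have a rationale. Rule 3 patients have encounters after supply end, so they were demonstrably still observed over the covered days. Rule 5 patients have none, the source is contributing hospitals only, and the last encounter is the last date on which observation is certain. If they had moved elsewhere, their later events are unseen, and carrying them to supply end would understate rates by about 5-9% at 60-day supplies. This stands. A reader might infer that supply-end censoring should simply replace rule 5 for everyone. The documents do not support that, because for patients who left it exchanges one possible bias for another.

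A reader might also infer that the plan states that patients at the data cut go back to their last visit. It does not. No rule names the cut, and the 45-day condition cannot be assessed when that window runs past the end of the data. The gap is a missing rule; rule 5 reaches these patients only because it is the one that literally fits. But the event-capture objection does not protect the current text here, because these patients are still observed up to the cut.

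Finally, a reader might infer that the treatment comparison is biased. That needs a difference between arms that the documents do not report. INR visits make it plausible for warfarin, but intermediate visits of any kind also shorten the lost interval. With 60-day against 30-day supplies the shift is at most about 5% (0.695/0.663 = 1.048), small beside the sampling error at 246 events: 95% limits of a factor exp(1.96 × 2/√246) = 1.28.

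**Conclusion.** The asymmetry is real and follows from the text of rules 1, 2 and 5. Its direction for incidence rates is upward in both arms; its size rests on inputs that the documents do not give. At 30- to 60-day supplies the data-cut patients contribute about 1-3%, and below 1% if supplies are 30 days and entry is spread over the whole data set. Patients who left the database contribute from about zero, when none of their later events is captured, up to a total of about 6-11% at 60-day supplies with full capture. The hazard ratio is essentially unaffected unless supply length, visit spacing or the share ending under rule 5 differs by arm. The power calculation is untouched. The data-cut gap has a clear remedy; for patients who left, neither censoring date is right in all circumstances, so the uncertainty should be shown.

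**What to change.** In SAP 4.1.3.1 and protocol 9.2:

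1. Add a data-cut rule. Patients still within their supply, or its 45-day window, at the end of the data set are followed to the earlier of supply end and the data cut, within the two-year cap, and not back to the last encounter. State a valid cut date, since the documents print 31 June.
2. For patients who left the database before the cut, report the primary rates and hazard ratios under both last-encounter and supply-end censoring, as a bracket. Each can be biased, in opposite directions, depending on how many later events are captured.
3. Report by arm the share ending under rule 5 and the median days of supply, so that readers can judge whether the hazard ratio could be affected.

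The cost is one added rule, one repeat of the primary analyses and two descriptive lines, all from data already being extracted.

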4.1.3.2. Index date

The date when patients initiated warfarin or apixaban

4.2. SAFETY ANALYSIS SET

Safety-related events other than bleeding will not be collected for this analysis. As mentioned above, bleeding will be investigated as safety-related primary endpoints. However, other adverse events,

PFIZER CONFIDENTIAL

Page 10 of 56

serious AE or non-serious AE will not be collected in this analysis because the dataset provided by MDV will not contain the AE-related information.

4.3. OTHER ANALYSIS SET

None

4.4. SUBGROUPS

Following subgroups will be created and exploratory analyses for primary endpoints (major bleeding or stroke/SE) will be performed.

Variable	categories
Hypertension diagnosis	Yes or No
Liver dysfunction diagnosis	Yes or No
Renal impairment diagnosis	Yes or No
Bleeding diagnosis including intracranial hemorrhage	Yes or No
Treated with antiplatelet drug (>28d)	Yes or No
A go	>80 years
Age	>90years
Peptic ulcer diagnosis	Yes or No
Cancer diagnosis	Yes or No
Low body weight	<40 kg
Diabetes mellitus diagnosis	Yes or No
Polypharmacy	≥ 6 concomitant drugs

5. ENDPOINTS AND COVARIATES

5.1. EFFICACY/EFFECTIVENESS ENDPOINT(S)

Variable	Role	Operational definition		
Stroke/SE (composite) event after index date	Outcome (primary endpoint)	Operational definition of Stroke and SE will follow the operational definition of Stroke event after index date and SE event after index date. Time to events will be defined as the number of days from the index date to the occurrence of the first stroke or SE.		
Ischemic stroke event after index date	Outcome (secondary endpoint)	Ischemic stroke after index date not including the index date will be identified using hospital claims which had an ischemic stroke diagnosis code as the first listed ICD-10 diagnosis code (Appendix, 10.3.3). An event occurrence of ischemic stroke is defined as a case that "01: Disease name which input the most medical resources", "02:Sub-disease name", "11: Main disease name", "21: Disease name behind hospitalization", or "31: Disease name which input the second most medical resources" in DPC database. Time to ischemic		

Variable	Role	Operational definition	
		stroke will be defined as the number of days from the index date to the occurrence of the first ischemic stroke.	
Hemorrhagic stroke event after index date	Outcome (secondary endpoint)	Hemorrhagic stroke after index date not including the index date will be identified using hospital claims which had a hemorrhagic stroke diagnosis code as the first listed ICD-10 diagnosis code (Appendix, 10.3.3). An event occurrence of hemorrhagic stroke i defined as a case that "01: Disease name which input the most medical resources", "02:Sub-disease name", "11: Main disease	
SE event after index date Outcome (secondary endpoint)		SE after index date not including the index date will be identified using hospital claims which had a SE diagnosis code as the first listed ICD-10 diagnosis code (Appendix, 10.3.3). An event occurrence of SE is defined as a case that "01: Disease name which input the most medical resources", "02:Sub-disease name", "11: Main disease name", "21: Disease name behind hospitalization", or "31: Disease name which input the second most medical resources" in DPC database. Time to SE will be defined as the number of days from the index date to the occurrence of the first SE event.	

